Investigators and Trial Centres: The overall design and conduct of this investigator-initiated study will be the responsibility of the Steering Committee. This a collaborative trial designed and coordinated jointly by independent investigators at the National Institute of Health Innovation (University of Auckland), the Dept. of General Practice and Primary Care (University of Auckland), and Auckland District Health Board, with input from clinicians at Auckland DHB, Counties Manukau DHB, Waikato DHB, the Nurse Maude Association Christchurch, and the Southern DHB. Publication of data from this trial will be the responsibility of the Steering Committee. The trial will be co-ordinated from the NIHI, with participants recruited from patients attending the district nursing services at Auckland DHB, Counties Manukau DHB, Waikato DHB, the Nurse Maude Association Christchurch, and the Southern DHB.

Trial Period: Oct 2014 – Oct 2017

Clinical Phase: Phase III

Objectives: The objective of this trial is to determine the effectiveness of low dose aspirin compared to placebo when used in addition to compression therapy for venous leg ulcer healing.

Duration of Treatment: The maximum duration of treatment is 24 weeks (or less if the ulcer heals within 24 weeks).

Trial Design and Methodology

A prospective community-based, double-blind, placebo-controlled, randomised trial with participants receiving either 150 mg aspirin daily for up to 24 weeks or matching placebo. Block randomisation will be used, stratified by trial centre and prognostic index (ulcer size and duration) to ensure a balance of participants within trial centres and for participants likely to be slow healers. Participants in both arms will also receive compression therapy (with system of choice guided by patient and/or clinical preference) as delivered through district nursing services at the trial centres. Assessment of health-related quality of life will be carried out at baseline and at the end of the trial treatment period. The patient will continue to receive district nursing care as per normal protocol.

Inclusion/exclusion criteria: Patients with leg ulcers will be eligible for *inclusion* if they meet the following criteria:

- Aged 18 years or older
- Determined to have a venous leg ulcer (clinical indications of venous ulceration, ABI \geq 0.8, and other causative aetiologies ruled out)
- Able to tolerate compression therapy
- Able to provide written informed consent

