2.8 Rationale for a clinical trial

The ageing population and substantial anticipated increase in people with VLU (especially in the very old), the need for cheap, accessible adjuvant treatments, the role of platelets in the pathophysiology of VLU and the encouraging evidence for aspirin all point to the need for a definitive randomised controlled trial of low dose aspirin as an adjuvant treatment for VLU using a trial population that is as open as clinically possible and thus similar to that encountered every day in clinical practice.

[figure not shown]
3. Objectives

The main aim of this trial is to evaluate the effectiveness of low dose aspirin compared to placebo when used in addition to compression therapy for VLU time-to-healing over 24 weeks follow up. Other aims include estimating the effect of aspirin on proportion of patients healed, adverse events, adherence and health-related quality of life (HRQoL).

4. Trial Design

A prospective community-based, double-blind, placebo-controlled, randomised trial with participants receiving either 150 mg aspirin daily for up to 24 weeks or matching placebo. Block randomisation will be used, stratified by trial centre and prognostic index (ulcer size and duration) to ensure a balance of participants within trial centres and for participants likely to be slow healers. Participants in both arms will also receive compression therapy (with system of choice guided by patient and/or clinical preference) as delivered through district nursing services at the trial centres. The district nurse will identify potential participants, obtain verbal consent from them to be contacted by the research nurse if the patient is interested in the trial and notify the research nurse at each trial centre.

5. Trial Plan Schematic

6. Recruitment

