9.1 Primary outcome measure

Time to complete healing (defined as intact skin without a scab) is recommended as an outcome to be included in research by the Cochrane Collaboration Wound Review Group and a 24 week follow up period is considered a minimum. Time to event data will be obtained from clinical records. District nurses visit patients on a weekly basis as part of normal care and record healing (average number of district nurse visits was 1.1 per week in the HALT trial). At 24 weeks, the Research Nurse will determine if the reference ulcer is healed. If the reference ulcer is healed, the research nurses will access clinical records to determine the date of healing was first reported during the 24-week period. If the reference ulcer is unhealed, the Research Nurse will determine from the clinical record whether the reference ulcer had healed at any time prior to 24 weeks. If there is no mention of healing then the ulcer will be assumed to have been unhealed during the 24 weeks. If the reference ulcer is recorded as healed during that time, the unhealed ulcer will be assumed to be a recurrent ulcer and the date healing is first recorded will be assumed to be the healing date.

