9.2 Secondary outcome measures

The following secondary outcome measures will be assessed in all participants at 24 weeks after randomisation:

- Proportion of participants with a healed reference VLU at 24 weeks.

- Estimated change in ulcer area – obtained from measuring maximum width and length of reference ulcer at baseline and endpoint and the ulcer area at each time point estimated using the calculation for area of an ellipse.⁵⁰ See rationale above for not using more complex methods of ulcer measurement.
- Change in HRQoL: Measured at baseline and at 24 weeks. Each person's perception of his or her general health will be assessed using the RAND 36-item Health Survey (a version of SF-36), EQ5D and ulcer-related health using the CXVUQ.^{51,52} The EQ5D and SF-36 are well-validated questionnaires for assessing quality of life in New Zealand and generating utility values for economic analyses.^{53,54 55,56} However, they may not be as responsive as a disease-specific instrument to changes in ulcer state (healed *versus* unhealed) over the short-term.^{22,57} Consequently, the CXVUQ will also be used, as it has been found to be very responsive to changes in VLU healing state.²²
- Adverse events: Measured throughout the 24-week follow up. Standard definitions of adverse events will be used and adverse events reports will be reviewed by one of the medically-qualified co-investigators and coded using the ICD-10 AM. All participants will be issued with a Clinical Trial Card, stating their participation in the trial and the possibility they are receiving low dose aspirin. If the participant presents with signs and symptoms of a serious adverse event, such as myocardial infarction, stroke, or extra-cranial bleed, the Clinical Trial Card will recommend they discontinue trial treatment and appropriate treatment initiated. These participants will still be included in follow up at 24 weeks.
- Treatment adherence: Measured at 24 weeks by count of remaining capsules by the Research Nurse.
- Efficacy of blinding: Measured at 24 weeks, the efficacy of blinding will be tested by asking patients which treatment they believed they received, and asking the same question of the research nurses.

10. Data collection and follow-up

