10.6 Visit 3: 24 weeks after randomisation

- Determine if reference ulcer healed
- Obtain date healed from clinical record if healed
- Review concomitant medication and record compression system in use.
- Obtain remaining trial medication and count capsules.
- Carry out assessments of health-related quality of life (RAND 36, EQ5D, and CXVUQ).
- Assess blinding.
- Complete an "End of Trial Participant" survey to give feed-back on their trial experience.

11. Statistical Considerations

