11.1 Sample Size

We estimate that 354 participants will be required. A sample size of 318 would be sufficient to show a **four week** difference in time-to-healing at 90% power with an alpha of 0.05, assuming the median time-to-healing in the control group over a six month follow up is 92 days (the median time to healing suggested by a previous bandaging trial for VLU patients over 24 weeks).⁶⁰ These data equate to a hazard ratio for VLU healing of 1.45, which is smaller than that suggested by our re-analysis of data from a cohort in a previous VLU trial (hazard ratio for VLU healing 1.77 for 150 mg dose). A four week difference was the minimal important difference that would most frequently

persuade people to use aspirin in a small commissioned survey of older people in Auckland, was the time interval used in a Canadian venous ulcer trial (<http://clinicaltrials.gov/ct2/show/study/NCT00202267>) and is lower than clinically significant differences used to calculate the sample sizes in two large venous ulcer trials conducted in the United Kingdom (the VenUS II and III trials^{61,62}). Although both the HALT trial and the PREPARE Pilot achieved very high follow up rates (99% and 100%),^{8,34} we have allowed for 10% loss to follow up, and thus a sample of 354 (177 in each group) will be required. Even if recruitment were lower than anticipated, using the same assumptions as above, a sample of 238 inflated to 264 (132 in each group) to allow for 10% loss to follow up would be sufficient to show a four week difference in time to healing with 80% power with an alpha of 0.05.

We assume that 70% of patients presenting with leg ulcers to the trial centres will have VLU. This assumption is supported in the literature^{5,6} and in an audit of patients presenting to the Nurse Maude Association in Christchurch in 2010 (pers. comm., [name], see below).

- In Auckland DHB, the most recent data (2011) shows the service received 309 referrals from multiple sources (mainly general practitioner and internal sources). Extrapolating this data to the 18 month recruitment period, Auckland DHB would receive 463 new assessment requests of which 324 new patients would have VLU, assuming 70% of these referrals had venous ulceration.

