13.2.2 Notification of serious adverse events

Timely and complete reporting of all SAEs is necessary to identify events that are treatment related or potentially treatment related, thereby allowing: (1) a greater understanding of the overall safety profile of the treatment; (2) appropriate modification of trial protocols; and (3) adherence to regulatory requirements.

SAEs are to be documented on a CRF X and reported to the project manager within one day (24 hours) of detection. Participant deaths or SAEs that occur within 30 days after stopping the trial treatment should also be reported.

All CRF Xs require sign off by the authorised medical practitioner at NIHI who will assess the AE (blinded to treatment allocation) to determine whether the AE is a possible SAE.

If the AE is a possible SAE, the participant will be withdrawn from treatment, the trial treatment collected by the research nurse and the possible SAE will be notified to the participant’s GP.

The Principal Investigator will have the overall responsibility of ensuring that all events are reported to the regulatory authorities in the appropriate timeframes. The project manager will have the responsibility to ensure that SAEs are appropriately monitored and reported. As participants with AEs will not be unblinded during the trial, there will be no expedited reporting on serious suspected adverse drug reactions.

Participants experiencing AEs that cause interruption or discontinuation of trial treatment, or those experiencing SAEs that are present at the end of their participation in the trial will receive follow-up as appropriate, which may involve referral to the participant’s general practitioner.

All AEs will be classified by a medical coder at the NIHI who will be blind to treatment allocation. Standard definitions of adverse events will be used and graded using the Common Terminology Criteria for Adverse Events v3.0.

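### Does a single leftover-capsule count at week 24 make the adherence outcome depend on how fast the ulcer heals?

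*Protocol*

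**What the plan says.** Adherence is a secondary outcome in the synopsis and in Section 9.2, which defines it in one line: "Treatment adherence: Measured at 24 weeks by count of remaining capsules by the Research Nurse". The schedule in Section 10.2 marks the pill count at week 24 only, and the Section 10.6 task list agrees: "Obtain remaining trial medication and count capsules".

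Sections 14.2 and 14.3 give each participant a 168-day supply at randomisation, in one bottle. The synopsis sets the treatment period: "The maximum duration of treatment is 24 weeks (or less if the ulcer heals within 24 weeks"). Section 4 has "participants receiving either 150 mg aspirin daily for up to 24 weeks or matching placebo", which is compatible with that but does not mention healing.

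The healing date is collected for the primary outcome. Under Section 9.1, where the ulcer is healed at week 24, "the research nurses will access clinical records to determine the date of healing was first reported during the 24-week period"; where it is open again, the first recorded healing date is used. Section 10.6 repeats the item. The only earlier retrieval of capsules described follows a possible serious adverse event (Section 13.2.2): "the participant will be withdrawn from treatment, the trial treatment collected by the research nurse". No section lists a date of last capsule, and none gives a denominator for adherence.

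**The concern.** Planned exposure depends on the primary outcome. If capsules returned are compared with 168, someone who heals early and stops as planned looks non-adherent. If aspirin works, its arm heals sooner, returns more capsules and looks less adherent, although nobody missed a dose.

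Putting days to healing in the denominator may not cure this completely. Take a participant who healed on day 64 and returns 104 capsules. They may have taken one a day and stopped (64/64 = 100%), or continued to day 168 while taking 64/168 = 38%. Count and healing date are identical in the two cases, so no later analysis of those two items can separate them. At stake is a secondary process measure that readers use to judge whether the treatment was given a fair test.

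**Working it through.** **Inputs.** Supply 168 days (Section 14.2), which matches 24 × 7 = 168. Control median from Section 11.1: "assuming the median time-to-healing in the control group over a six month follow up is 92 days". The target difference is four weeks, so the aspirin median is 92 − 28 = 64 days and the hazard ratio 92/64 = 1.44, close to the stated 1.45. Assumptions, because the documents give no figures: exponential healing times, a steady daily adherence p, and a share f of healed participants who continue to day 168.

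**1. Bare count or 168 as denominator; all adherent, all stop at healing (p = 1, f = 0).** With λ = ln 2 / median, mean days on treatment = (1 − exp(−168λ))/λ.

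| | Placebo | Aspirin |
|---|---|---|
| Healed by day 168 | 71.8% | 83.8% |
| Mean days on treatment | 95.3 | 77.4 |
| Mean capsules left | 72.7 | 90.6 |
| Share of 168 | 56.7% | 46.1% |

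The false gap is 17.9 capsules, or 10.7 points.

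**2. Days to healing as denominator, same behaviour.** Each ratio is 1, so both arms read 100% and the gap is zero.

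**3. Some continue after healing.** Let F be the share healed by day 168 and T the healing time. A continuer takes 168p capsules against a denominator of T. With each person's ratio capped at 100%, the arm mean is p(1 − fF) + f·E[min(1, 168p/T); T ≤ 168]. With 168 as denominator, it is p × (mean days on treatment)/168, where mean days = (1 − f) × 95.3 + 168f on placebo, and likewise with 77.4 on aspirin.

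| p | f | Healing date, capped: placebo v aspirin | Gap, points | Against 168: placebo v aspirin | Gap, points |
|---|---|---|---|---|---|
| 80% | 25% | 83.4 v 84.0 | 0.6 | 54.0 v 47.6 | 6.4 |
| 80% | 50% | 86.8 v 88.0 | 1.3 | 62.7 v 58.4 | 4.3 |
| 60% | 25% | 66.2 v 67.5 | 1.3 | 40.5 v 35.7 | 4.8 |
| 60% | 50% | 72.3 v 74.9 | 2.6 | 47.0 v 43.8 | 3.2 |

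**4. Without the cap.** Pooled capsules taken over pooled days to healing, at p = 80%: 95.3% v 103.4% for f = 25%, and 110.5% v 126.9% for f = 50%. These gaps, about 8 and 16 points, exceed those with 168 as denominator. Values above 100% show at once that the ratio is being misread.

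**5. Can continuers be recognised?** A continuer shows up when capsules taken exceed days to healing, that is when T < 168p. At 80% adherence the limit is 134.4 days, and 11% (placebo) and 8% (aspirin) of healed participants fall between it and day 168; at 60% the limit is 100.8 days and the shares are 26% and 21%. Most continuers therefore stand out.

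**6. No treatment effect.** With equal healing-time distributions and equal continuation, all these formulas give the same value in both arms. The between-arm distortion arises only if healing times or continuation differ.

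**The case for a change.** The strongest case for acting is that a missing denominator can be supplied later, but an item never collected cannot. On the protocol's listing, the day-64 ambiguity is permanent. The healing date also cannot be said to remove most of the problem in general: at 60% adherence with half continuing, the capped gap of 2.6 points is little better than the 3.2 points against 168, and adherence is overstated by 12 to 15 points. One extra field at an existing visit is cheap, and Section 13.2.2 seems to need a stop date as well: "Participant deaths or SAEs that occur within 30 days after stopping the trial treatment should also be reported".

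The logical point stands: count and healing date alone do not identify adherence in those who continue. It does not carry the conclusion, for four reasons.

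- A last-capsule date is a case-report-form item. The schedule names the forms and an end-of-trial survey, but their contents are not shown, so absence from the protocol text does not establish that it goes unrecorded.
- The large effects need many participants to continue past the end of treatment given in the synopsis. Nothing in the documents supports a particular share.
- The remedy is weaker than it looks. A healer at day 64 would be recalling a date 168 − 64 = 104 days later. Extending the denominator to the last capsule counts days after healing as doses due: 64 of 64 to healing, then ten stray capsules up to day 164, scores 74/164 = 45%.
- The 30-day rule concerns safety reporting, and it does not alter what the adherence count can show.

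Nor do the sections conflict on treatment length. A period of up to 24 weeks accommodates an end at healing, Section 9 lists reasons for withdrawal rather than planned completion, and Section 10.6 is a list of visit tasks.

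**Conclusion.** The concern does not call for a change. The 18-capsule, 10.7-point artefact requires a bare count or a denominator of 168 that the protocol does not prescribe, and an analyst holding the healing date would have good reason not to use either. For participants who stop at healing, the collected data remove the artefact entirely.

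The remainder is real but small: a false between-arm gap of 0.6 to 1.3 points at 80% adherence with 25% to 50% of healed participants continuing, and 1.3 to 2.6 points at 60%, with ratios capped at 100%. The cap matters; without it the healing-date ratio misleads by more than the crude one. The level of adherence would be overstated in both arms, by 3 to 8 points at 80%, and that should be remembered when the figure is read. These sizes rest on exponential healing at the planning medians and on assumed adherence and continuation. A single pill count is a fair trade-off for a secondary process measure in a community trial without a research visit at healing. The intention-to-treat primary analysis and the sample size of 354 do not depend on it.

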10.1 Baseline assessments

Screening information will be obtained from a telephone contact with the patient at week -1. Eligible patients will be visited at Week -1 and, once consented, the following baseline data will be collected immediately prior to randomisation:

- Demography: age, sex, self-reported ethnicity.
- Ulcer area and duration: Reference VLU area (area > 5 cm²) and duration (duration for > six months) provide data for a prognostic index for VLU healing with 24 weeks of compression.⁵⁸ The index assigns scores of 0, 1 or 2 based on absence of both factors, presence of one factor, or presence of both factors. Sophisticated tools for measuring ulcer area are either too expensive (e.g. SilhouetteTM) or no longer supported by the manufacturer in New Zealand (e.g. VisitrakTM). A simpler method of estimation using the formula for area of an ellipse has been shown to be highly correlated with ulcer area, both in the literature ($r = 0.951$)⁵⁰ and internal data from one of our previous trials ($r = 0.92$).⁸ Ulcer duration will be obtained from patient recall. Where more than one VLU is present, the largest ulcer will be the reference ulcer.
- ABI: An ABI < 0.8 indicates that there is a high probability that some arterial insufficiency is present (positive predictive value = 95% in a general practice population).⁵⁹ Use of compression therapy where significant arterial disease is present can result in severe ischaemia in the leg,

with risk of necrosis. Consequently ABIs are routinely obtained for all patients with incident ulcers under the care of each of the trial centres taking part in the proposed trial, to confirm suitability for compression therapy. An ABI will be obtained from the clinical records for each participant. Where a potential participant already in treatment has an ABI obtained more than three months prior to the eligibility screen, a new ABI will be obtained prior to inclusion to ensure no development or progression of arterial disease.

- Clinical history and concomitant medications.
- Compression system: Details of the patient’s current treatment regime will be recorded.
- Health-related quality of life (HRQoL) instruments: The RAND 36-item Health Survey⁵¹, EQ5D,⁵⁴ and the Charing Cross Venous Ulcer Questionnaire (CXVUQ)⁵² will be administered.

10.2 Schedule of trial visits and procedures

	Visit 1	Phone/email contact	Visit 2	District Nurse	Visit 3 Research Nurse
Timing	Week -1	Week-1 to 0	Week 0	Weeks 1-24	Week 24
Case Record Form	A		B	X	E
General data					
Eligibility criteria	X		X		
Age & sex	X				
Ethnicity	X				
Informed consent	X				
Clinical history	X				
Record or obtain ABI	X				
Confirm safety with GP		X			
Confirm with participant visit 2		X			
Clinical information					
Concomitant medications			X		X
Compression system			X		X
Ulcer measurement (max W x L)			X		X
Other data collection					
Quality of life measures			X		X
Adverse events				X	X
Pill count					X
Testing blinding					X
End of trial participant survey					X
Treatment allocation					
Trial medication			X		

Form X will be completed by Research Nurse, but Research Nurse may be notified by District Nurse of possible adverse event.

10.3 Visit 1: Registration

- Answer any questions about trial.
- Obtain informed consent.
- Obtain patient’s name, date of birth, sex and self-reported ethnicity.

- Obtain relevant history for inclusion/exclusion
- Record or obtain ABI.
- Assess eligibility criteria.

10.4 Between Visit 1 and Visit 2

- Email/fax contact with participant's GP to confirm safe to receive aspirin
- Arrange visit 2 if patient eligible to receive aspirin.

